4.3 Duration of Treatment and Subject Participation

Subjects will continue treatment as long as clinically indicated as judged by the Principal Investigator (PI) of the study or the attending physician for up to 3 years. Treatment beyond 3 years may be permitted after discussion with the PI. The discussion should be documented in the subject's medical record.

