5.2 Dosing Delays

Up to a one month delay in the next dosing of Ruxolitinib, elected to be changed due to clinical side effects or laboratory abnormalities, is allowed.

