9.1 Disease Response Criteria

Clinical response will be assessed based on physical examination, CBC, a bone marrow aspiration, a whole body CT scan to be done at screening and 6 ± 2 months in accordance with the IWCLL guidelines (Hallek et al., 2008) as outlined in Table 8. If a 20% reduction in tumor burden is observed at 6 ± 2 months, Treatment will be continued as long as a CR, PR or at least a 20% reduction in tumor mass is achieved and sustained.

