10.0 CRITERIA FOR REMOVAL FROM THE STUDY

Patients will be removed from the study for the following reasons:

1. Pattern of noncompliance.
2. Toxicity (grade 3 or 4) inducing clinical symptoms necessitating red blood cell or platelet transfusions and not alleviated after dose adjustment.
3. Disease progression that require another therapeutic intervention (an increase in peripheral blood lymphocyte count is expected. If needed anti-CD20 antibody treatment (Rituximab or Ofatumumab) or leukopheresis are allowed).
4. Lack of response (a reduction of 20% of tumor mass or PR) at 6 ± 2 months.
5. Unexpected events (medical or other) that would prevent the patient from staying on study.
6. Patient's or physician's choice. Compliance will be assessed by the P.I. based on the drug accountability documented by the site staff and monitored by the designee. The objective is 100% compliance and the P.I. and his staff will evaluate compliance at each visit, and take appropriate steps to optimize compliance. For the purpose of subgroup analyses, subjects with at least 80% compliance over the total duration of dosing from the first day of dosing to the analysis of the study will be considered to be compliant.

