11.0 STATISTICAL CONSIDERATIONS

The study will be conducted at MDACC only. The primary endpoint will assess the clinical response (CR, PR, and a 20% reduction in tumor mass as assessed by a body scan and bone marrow aspiration/biopsy) at 6 ± 2 months after initiation of therapy.

We will incorporate an informal futility analysis when half of the total patients have reached 6 ± 2 months after initiation to assess whether the average change in the tumor mass score is less than zero (calculated as the score at enrollment minus the score at six months). If the average at this time is less than zero, the trial will be stopped early.

Because no treatment is the standard of care for these patients, we will routinely analyze the outcome of our Ruxolitinib-treated patients at a 6 \pm 2 month interval and compare their clinical outcome to that of patient who elected to receive no treatment.

Table 9 shows the probability of stopping early under several different scenarios, as well as how the overall power is for the primary analysis is affected by early stopping. The operating characteristics were produced in R version 2.13.0 by simulating 5000 trials with 17 patients at the interim and 34 patients at the end of the trial, accounting for a 15% drop out rate. The simulations stop early if the average change at 6 months is less than zero, and formally tests whether the change is not equal to zero at the final analysis using a paired *t*-test.

Table 9. Operating characteristics

True tumor burden difference (baseline score minus score at 6 months)	True SD of the Difference	Prob(Stop Early)	Power for Final Analysis
-1	2	0.9818	0.0026
0	2	0.5068	0.0218
1	2	0.0202	0.8064
2	2	0.0000	0.9998
-1	4	0.8398	0.0014
0	4	0.4958	0.0274
1	4	0.1584	0.2876
2	4	0.0198	0.8074

For primary analysis, the paired *t* test will be used to evaluate the changes of tumor burden from baseline to 6 \pm 2 months after initiation of therapy. Response rate will be estimated with 95% confidence interval. Patients who drop out early will be counted as non-responders. The Kaplan-Meier method will be used to estimate time to next treatment, and will compared to our historical data (Wierda et al., 2011) using Cox proportional hazards model, adjusting for effects of covariates. If necessary and applicable, appropriate methods such as propensity score matching will be used to match the patients of this study with the historical data to reduce comparison bias.

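### The 80% compliance rule for subgroup analyses counts dosing after the 6-month endpoint, over a window whose length depends on response

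*Combined protocol and SAP*

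**What the plan says.** Section 10, item 6 introduces a compliance classification "For the purpose of subgroup analyses" and counts as compliant "subjects with at least 80% compliance over the total duration of dosing from the first day of dosing to the analysis of the study". It is the only definition in the document. Section 11, the statistical section, neither repeats nor replaces it and names no particular compliance subgroup analysis.

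The other relevant provisions are:

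- **Endpoint time.** Section 11: "The primary endpoint will assess the clinical response", timed "at 6 ± 2 months after initiation of therapy".
- **Who stops.** Section 10, item 4 lists as a reason for removal "Lack of response (a reduction of 20% of tumor mass or PR) at 6 ± 2 months".
- **Who continues.** Section 9.1: "Treatment will be continued as long as a CR, PR or at least a 20% reduction in tumor mass is achieved and sustained".
- **How long.** Section 4.3 leaves duration to the judgement of the principal investigator "or the attending physician for up to 3 years", and longer after discussion with the principal investigator.
- **Holds.** Section 5.2 allows "Up to a one month delay in the next dosing of Ruxolitinib" for side effects or laboratory abnormalities. Section 4.1 requires dose adjustment for specified toxicities and falling counts.
- **Data.** Section 4.2 has site staff count returned tablets at study visits and record the result on the case report form.

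**The concern.** A variable used to split patients in an analysis of a 6-month outcome should be fixed by the time that outcome is read. This one is not, for two reasons. First, Section 10 item 4 and Section 9.1 make continued dosing conditional on the 6-month result, so the outcome helps to set how long a patient's compliance is measured. Second, for patients still on drug, tablets taken or missed after the scan count towards the label.

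Two patients with identical intake up to the assessment can therefore fall in different groups, only because one responded and went on to be observed for longer. A difference in 6-month response between compliant and non-compliant patients could then appear when intake and response are unrelated, or a real difference could be masked. At stake is how any such subgroup comparison is read.

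**Working it through.** The plan gives no compliance figure to reproduce beyond the 80% cut. The nearest numerical claim is Table 9, checked here only to see whether the design depends on the label. For a true difference of 1 and SD 2, the probability of stopping early is Φ(−1 × √17 / 2) = 0.0196, against 0.0202 stated. Simulated power (100,000 trials, n = 34, two-sided paired t-test, alpha 0.05 assumed because none is stated) is 0.807, against 0.8064 stated. Also 34 / (1 − 0.15) = 40. Compliance enters none of these.

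**Step 1: window length.** A patient removed for lack of response has a window ending at 4 to 8 months. A responder dosed for T months has a share (T − 6)/T of the window after a month-6 assessment: 50%, 75% and 83% for T = 12, 24 and 36. With T = 36 and the assessment at month 4 or 8, the share is 89% or 78%. T is an assumption: Section 4.3 caps routine treatment at 3 years, but no analysis date is given.

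**Step 2: effect on the score.** Let c1 be compliance in months 0–6 and c2 compliance afterwards (both assumed). Score = (6·c1 + (T − 6)·c2) / T.

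- c1 = 95%, c2 = 70%, T = 36: (5.7 + 21.0)/36 = 26.7/36 = 74%. Non-compliant, although at 95% when the endpoint was read.
- c1 = 60%, c2 = 90%, T = 36: (3.6 + 27.0)/36 = 30.6/36 = 85%. Compliant. A non-responder with the same 60%, removed at month 6, is non-compliant.
- The same 60%-then-90% patient scores 9.0/12 = 75% at T = 12 and 19.8/24 = 82.5% at T = 24, so the label changes with the analysis date.

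**Step 3: break-even later compliance.**

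- A patient at 95% early becomes non-compliant if c2 falls below (0.8T − 5.7)/(T − 6): 65%, 75% and 77% at T = 12, 24 and 36.
- A patient at 60% early becomes compliant if c2 reaches (0.8T − 3.6)/(T − 6): 100%, 87% and 84%.

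**Step 4: effect on a subgroup comparison.** An illustrative simulation assumed no association between response and compliance in months 0–6. Other assumptions were 40% response, early compliance with mean 85%, an SD of 12 points early and late, an early–late correlation of 0.5, responders dosed 12 to 36 months and non-responders to month 6.

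| Mean later compliance | Response, compliant | Response, non-compliant | Responders whose label changes |
|---|---|---|---|
| 75% | 29% | 54% | 32% |
| 80% | 36% | 47% | 25% |
| 85% | 41% | 39% | 23% |
| 90% | 44% | 30% | 23% |

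Label changes are relative to a window ending at month 6; no non-responder changes label. With that shorter window, response is about 40% in both groups in every row, as it should be.

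**Step 5: denominator.** The definition does not say whether doses held under Section 5.2 count as planned. If they do, a one-month hold gives 90/120 = 75% for a window ending at month 4, 150/180 = 83% at month 6 and 11/12 = 92% at month 12. If they do not, the hold has no effect.

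**The case against.** The strongest reply is that no harmed analysis is written down. Section 11 specifies no compliance comparison, endpoint or test, and the documents never say what the subgroup is meant to show. That stands. The point is about a stated rule that would give a misleading answer if used on the 6-month endpoint.

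A second reply is that the window's end could mean the 6-month analysis. The text does not say so. A study-level analysis also falls on a calendar date, so responders enrolled earlier would still contribute later dosing. Section 11 describes a halfway look, routine comparisons and a final analysis, so the date is not unique.

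A third is that 70% intake for 30 months is unlikely: Section 10 removes patients for a pattern of noncompliance, aims for 100% and reviews intake at each visit. This stands in part. The example is illustrative, and at T = 12 the same rates give (5.7 + 4.2)/12 = 82.5%, still compliant. But no numerical threshold for removal is given, and at T = 36 later intake below 77% is enough to change the label.

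A reader might infer more than the documents support:

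- *That the bias mainly hides a link between adherence and response.* It does not have a fixed direction. The simulated difference reverses sign as later compliance rises from 75% to 90%, and nearly vanishes at 85%.
- *That patients who follow the protocol fall below 80%.* This depends on an unstated denominator, and in the example only the window ending at month 4 fails.
- *That the main efficacy result is compromised.* The paired t-test and response rate do not use the label.

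**Conclusion.** The point holds within limits. As written, the classification depends partly on the 6-month response, through window length, and on behaviour after it. A comparison of 6-month response or tumour-burden change by compliance would condition on post-outcome information. This follows from Sections 4.3, 9.1 and 10 alone.

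The size rests on assumptions. With 36 months of dosing, 83% of a responder's window lies after month 6. With no true association, the simulated comparison ranged from 29% versus 54% to 44% versus 30%, depending on assumed later compliance. The documents give no later-compliance data, so neither direction nor size can be predicted. Window length also depends on enrolment date, toxicity, withdrawal and data cut-off.

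The primary paired t-test, the response rate, the sample size and the power are unaffected. The definition should be corrected before any compliance subgroup result is reported.

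**What to change.** In Section 10 item 6, for subgroup analyses of the 6 ± 2 month endpoint, define compliance as tablets taken divided by tablets prescribed, with protocol-permitted holds and reductions already taken out of the prescribed number. Count from Day 1 to the 6 ± 2 month response assessment, or to permanent discontinuation if earlier, and apply the 80% cut to that figure. Report patients who discontinue before the assessment as a separate category, neither compliant nor non-compliant. Report later adherence descriptively.

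The separate category matters. On time actually dosed, someone who stops at week 3 having taken every tablet counts as compliant. Running the denominator on to the scheduled visit would instead give about 3/26 = 12% and label patients who stopped for toxicity or progression as non-compliant. Section 11 already counts early drop-outs as non-responders, so that choice would build in an association between adherence and response.

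The cost is a short text change, slightly more analysis work and a smaller set of patients in the compliant versus non-compliant comparison. The tablet counts are already collected under Section 4.2. Treatment, sample size and power do not change.

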11.0 STATISTICAL CONSIDERATIONS

The study will be conducted at MDACC only. The primary endpoint will assess the clinical response (CR, PR, and a 20% reduction in tumor mass as assessed by a body scan and bone marrow aspiration/biopsy) at 6 ± 2 months after initiation of therapy.

We will incorporate an informal futility analysis when half of the total patients have reached 6 ± 2 months after initiation to assess whether the average change in the tumor mass score is less than zero (calculated as the score at enrollment minus the score at six months). If the average at this time is less than zero, the trial will be stopped early.

Because no treatment is the standard of care for these patients, we will routinely analyze the outcome of our Ruxolitinib-treated patients at a 6 \pm 2 month interval and compare their clinical outcome to that of patient who elected to receive no treatment.

Table 9 shows the probability of stopping early under several different scenarios, as well as how the overall power is for the primary analysis is affected by early stopping. The operating characteristics were produced in R version 2.13.0 by simulating 5000 trials with 17 patients at the interim and 34 patients at the end of the trial, accounting for a 15% drop out rate. The simulations stop early if the average change at 6 months is less than zero, and formally tests whether the change is not equal to zero at the final analysis using a paired *t*-test.

Table 9. Operating characteristics

True tumor burden difference (baseline score minus score at 6 months)	True SD of the Difference	Prob(Stop Early)	Power for Final Analysis
-1	2	0.9818	0.0026
0	2	0.5068	0.0218
1	2	0.0202	0.8064
2	2	0.0000	0.9998
-1	4	0.8398	0.0014
0	4	0.4958	0.0274
1	4	0.1584	0.2876
2	4	0.0198	0.8074

For primary analysis, the paired *t* test will be used to evaluate the changes of tumor burden from baseline to 6 \pm 2 months after initiation of therapy. Response rate will be estimated with 95% confidence interval. Patients who drop out early will be counted as non-responders. The Kaplan-Meier method will be used to estimate time to next treatment, and will compared to our historical data (Wierda et al., 2011) using Cox proportional hazards model, adjusting for effects of covariates. If necessary and applicable, appropriate methods such as propensity score matching will be used to match the patients of this study with the historical data to reduce comparison bias.

Continuous variables will be summarized using descriptive statistics such as mean, standard deviation, median and range. Categorical variables will be tabulated by

frequencies and the corresponding percentages. The Fisher's exact test or logistic regression analysis will be used for any binary outcomes. Statistical t-tests or Wilcoxon rank sum tests will be used to compare continuous variables. Longitudinal analysis may be used to model the change in tumor burden.

A Toxicity/Efficacy Summary will be submitted to the IND Office Medical Affairs and Safety Group, after the first five evaluable subjects complete 6 to 8 months from treatment initiation, and every five evaluable subjects thereafter.

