1.0 OBJECTIVES

1.1 Primary Objectives

To determine the effect of ruxolitinib in patients with high-risk CLL/SLL who do not require anti-neoplastic therapy according to the IWCLL 2008 recommendations and were either previously untreated or treated with Ibrutinib for less than 3 months and were deemed Ibrutinib intolerant: a.) On disease burden, and b.) The rate of complete response (CR) and partial response (PR) as assessed by the IWCLL 2008 response criteria.

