8.3 Disease Response Assessment

Assessment of clinical response will be conducted in accordance with our standard of care (physical examination, CBC, a bone marrow aspiration, and a whole body CT scan to be done at screening and 6 ± 2 months into treatment).

The IWCLL response criteria (Hallek et al., 2008) (Table 8) will be used to assess disease response. A bone marrow aspiration, a whole body CT scan is to be done at screening and 6 ± 2 months into treatment to further assess response. If a 20% reduction in tumor burden is observed at 6 ± 2 months, Treatment will be continued.

Table 8. Response definition after treatment for patients with CLL/SLL, using the parameters of Tables 1 and 3

Parameter	CR*	PR*	PD*
Group A			
Lymphadenopathy [‡]	None > 1.5 cm	Decrease \geq 50%	Increase \geq 50%
Hepatomegaly	None	Decrease \geq 50%	Increase \geq 50%
Splenomegaly	None	Decrease \geq 50%	Increase \geq 50%
Blood lymphocytes	< 4000/ μ L	Decrease \geq 50% from baseline	Increase \geq 50% over baseline
Marrow [‡]	Normocellular, < 30% lymphocytes, no B-lymphoid nodules. Hypocellular marrow defines CRi (5.1.6).	50% reduction in marrow infiltrate, or B-lymphoid nodules	
Group B			
Platelet count	> 100 000/ μ L	> 100 000/ μ L or increase \geq 50% over baseline	Decrease of \geq 50% from baseline secondary to CLL/SLL
Hemoglobin	> 11.0 g/dL	> 11 g/dL or increase \geq 50% over baseline	Decrease of > 2 g/dL from baseline secondary to CLL/SLL
Neutrophils [‡]	> 1500/ μ L	> 1500/ μ L or > 50% improvement over baseline	

Group A criteria define the tumor load, group B criteria define the function of the hematopoietic system (or marrow).

[‡]* CR (complete remission): all of the criteria have to be met, and patients have to lack disease-related constitutional symptoms; PR (partial remission): at least two of the criteria of group A plus one of the criteria of group B have to be met; SD is absence of progressive disease (PD) and failure to achieve at least a PR; PD: at least one of the above criteria of group A or group B has to be met.

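### Section 11.0 leaves open whether the response rate for a primary objective counts only CR and PR, or also patients with a 20% fall in tumor mass

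*Combined protocol and SAP*

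**What the plan says.** Section 1.1 splits the primary objective in two. Part (a) is the effect on disease burden. Part (b) is "The rate of complete response (CR) and partial response (PR) as assessed by the IWCLL 2008 response criteria".

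Table 8 in Section 8.3 sets out CR, PR and PD, with 50% thresholds for the PR items on tumor load and no 20% category. Its footnote adds the remaining class: "SD is absence of progressive disease (PD) and failure to achieve at least a PR".

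Section 9.1 points to the same table: "Clinical response will be assessed based on physical examination, CBC, a bone marrow aspiration, a whole body CT scan", to be judged "as outlined in Table 8. If a 20% reduction in tumor burden is observed". The 20% figure there opens a new sentence, which is about whether treatment goes on.

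Section 11.0 describes the primary endpoint as "clinical response (CR, PR, and a 20% reduction in tumor mass", judged by scan and marrow at 6 ± 2 months. On analysis it says: "Response rate will be estimated with 95% confidence interval. Patients who drop out early will be counted as non-responders". It does not define a responder at that point.

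Two other places use the word response more widely. The opening of Section 9.0 counts a fall in tumor mass among the response criteria. Section 10.0, item 4, gives as a ground for removal "Lack of response (a reduction of 20% of tumor mass or PR" at 6 ± 2 months.

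**The concern.** A patient can be SD under Table 8 and still fall within what Section 11.0 calls clinical response. If that wording is carried into the response rate, SD patients enter the numerator of an estimate meant to answer objective 1.1(b). If it is not, the rate is CR plus PR. The plan does not say which.

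At stake are the estimate and confidence interval for one half of the primary objective. With two numerators available and no stated choice, the selection could be made once the results are known. A reader of the report could not tell whether a quoted rate means IWCLL response or something looser.

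**Working it through.** **The plan's own figure.** For a true difference of 1 and SD 2, Table 9 gives a stopping probability of 0.0202 and power of 0.8064. The check simulated 200,000 trials per row: 34 normally distributed changes, a stop if the mean of the first 17 is below zero, otherwise a paired t test. The wording of the test is two-sided. Alpha is not stated and was taken as 0.05. The results are 0.0195 and 0.8063, and all eight rows agree to within 1 percentage point. A one-sided 0.05 test would give 0.883 in that row, so the assumption fits the table. No responder definition enters this calculation: the powered analysis is the continuous change in tumor burden.

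**One patient under each section.** Take a patient at 6 ± 2 months with a 30% fall in tumor mass, PR not met and no PD criterion met.

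| Place | How the patient is treated |
|---|---|
| Objective 1.1(b) with Table 8 | SD, not counted |
| Section 9.1 | Classified by Table 8, so SD; the 20% figure bears on continuing treatment |
| Section 9.0, opening | Tumor mass reduction is among the response criteria; no rate is defined |
| Section 10.0, item 4 | Not a lack of response |
| Section 11.0, read literally | Within clinical response, counted |

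**Size per patient.** Section 11.0 gives 34 patients at the end of the trial after 15% dropout.

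- Enrolled: 34/(1 − 0.15) = 34/0.85 = 40. Tables 10 and 11 also run to 40.
- Early dropouts count as non-responders, so they stay in the denominator, which is 40.
- One reclassified patient: 1/40 = 2.5 percentage points.
- If k patients reach a 20% fall without CR or PR, the wide rate minus the narrow rate is k/40. CR and PR are in both numerators, so the wide rate can never be the lower one.

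The documents do not give k. As arithmetic on assumed counts only, not a forecast, suppose 4 of 40 have CR or PR. Intervals are exact (Clopper-Pearson).

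| Assumed k | Rate | 95% CI |
|---|---|---|
| 0 (CR + PR only) | 4/40 = 10.0% | 2.8% to 23.7% |
| 4 | 8/40 = 20.0% | 9.1% to 35.6% |
| 8 | 12/40 = 30.0% | 16.6% to 46.5% |
| 12 | 16/40 = 40.0% | 24.9% to 56.7% |

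**The case against.** The best defense is that Section 11.0 simply names both halves of the primary objective in one parenthesis: CR and PR for 1.1(b), tumor mass for 1.1(a). The analysis paragraph divides the same way, with a paired t test for burden and a confidence interval for the rate. Only objective 1.1(b) actually defines a rate; Table 8 sorts patients into classes and does not say which classes make up a rate. The plan also tabulates categorical variables, so CR, PR and SD counts should be recoverable, and no decision hangs on the rate.

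Much of this stands. A reader might infer that the plan formally defines the response rate twice. It does not: there is one definition, in 1.1(b), and a differently worded endpoint followed by an undefined rate. Nor is Section 9 wholly on the narrow side, given its opening sentence.

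The defense does not settle the matter. Section 11.0 does not say that its parenthesis lists two objectives, and Section 10.0, item 4, shows the protocol using response to include a 20% fall. That item is a removal rule, so it does not define the rate, but it makes the wider reading natural. Recoverable counts would let a reader compute CR plus PR; they would not say which rate the plan meant as its answer to 1.1(b).

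**Conclusion.** The concern holds as an unresolved conflict of wording that leaves two possible numerators for a primary-objective estimate. It should be fixed, but it does not undermine the design. Its size is 2.5 percentage points per reclassified patient, resting on 40 enrolled and on dropouts staying in the denominator.

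Three stronger readings are not supported:

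- **That power or the interim rule is compromised.** The paired t test, the futility rule, Table 9 and the sample size all use the continuous score, and Table 9 reproduces.
- **That the total gap between the two rates can be stated.** Table 9 is in score units. The documents give no distribution of percentage change in tumor mass, so any modelled gap would only reflect an assumed mean and SD.
- **That an expected lymphocyte rise makes Table 8 unworkable.** Table 8 says "PD: at least one of the above criteria of group A or group B has to be met", and a lymphocyte rise of at least 50% is one such criterion, while Section 10.0 expects some increase. But Section 2.1.1 describes counts that later fell to or below baseline, and nothing shows how often a rise of that size would persist at 6 ± 2 months. That is a separate, conditional question and not part of this point.

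**What to change.** Amend the opening sentence of Section 11.0 itself; adding a definition further down would leave the conflicting wording in place. It should name two separate endpoints at 6 ± 2 months:

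- **(a) Change in tumor burden**, analyzed by the paired t test. The proportion of patients whose tumor mass falls by at least 20% is reported separately under this heading and is not counted as response.
- **(b) Response rate**, defined as the proportion with CR or PR per Table 8, with a 95% confidence interval and early dropouts counted as non-responders.

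Add one sentence stating that the wider use of response in the opening of Section 9.0 and in Section 10.0, item 4, does not define this rate. The rules on continuing treatment and on removal in Sections 8.3, 9.1 and 10.0 are not changed by this.

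The cost is a few sentences. It needs no new data and no change to Table 8, the t test or the sample size. The study is closed to new entry, so only analysis and reporting are touched. The sponsor does have to accept that the 20% category, now listed inside the primary endpoint, moves to a separate line under (a), and that the headline response rate is likely to be lower than with that category included.
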